**c. Local Number of Subjects**

This is a pilot study which aims to enroll 30 patients locally, 15 per arm.

**d. Study Timelines**

We expect this study to be completed within one year of receiving IRB approval. We aim to achieve complete enrollment of 30 participants in a 6- to 9-month period. Following the completion of participant enrollment and data collection, the obtained results will be reviewed and statistically analyzed over a 3-month period. Finally, a manuscript detailing the study results will be written and submitted for publication.

**e. Study Endpoints**

Primary Outcome: Complete wound closure of a chronic, non-healing wound at 6 weeks.

- a. Complete wound closure will be defined as skin reepithelialization without drainage or dressing requirements confirmed at two consecutive study visits 2 weeks apart. Incidence of complete wound closure in the control group will be compared to that of the treatment group.

Secondary Outcome: Rate of wound closure over 6-week study period.

- a. PUSH Tool 3.0 scores and clinical photos will be compared between the control group and treatment group to evaluate the rate of wound closure over the course of the 6-week study period.

Tertiary Outcome: Compliance and patient satisfaction with immunonutrition supplementation regimen.

- a. Patient satisfaction surveys and compliance logs will be evaluated to assess feasibility of implementing an immunonutrition regimen into standard wound care.

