## 2) Objectives / Research Aims

Chronic, non-healing foot ulcers are a common complication of diabetes that can threaten loss of limbs, shorten life expectancy, and require resource-intensive treatment. Patients who exhibit these late effects of diabetes are often medically complex and have not only a shortened life expectancy but also a lower quality of life than their non-ulcer peers. Despite the prevalence of obesity in these patients, many exhibit metabolic signs of malnutrition, malabsorption, or both. Even when direct treatment for the ulcer is ideal, if the patient does not have the metabolic building blocks or the correct macronutrient healing environment, then treatment will be futile.

To this end, we believe focused immunonutrition supplementation consisting of L-Arginine, Omega-3 fatty acids, and Vitamin C combined with quality wound care will lead to an improvement in treatment success, satisfaction, patient reported outcome measures, and limb salvage.

**Specific Aim 1:** To compare the healing process of diabetic patients with chronic, non-healing, lower-extremity wounds receiving oral immunonutrition supplementation to patients receiving traditional care.

- a. This will be addressed by performing a prospective, randomized pilot study including 30 diabetic patients with chronic lower extremity wounds, Wagner stages 1-2. Fifteen patients will receive oral immunonutrition supplementation (2 grams omega-3 fatty acids + 500 mg vitamin C + 4.5 grams L-arginine per day) in addition to current standard of care and 15 patients will receive the current standard of care only. Study participation will continue for 6 weeks.
- b. Effect of wound healing will be assessed utilizing the Pressure Ulcer Scale for Healing (PUSH) Tool 3.0 which scores ulcers based on size ( $\text{cm}^2$ ), exudate amount, and tissue type present. Plantar pressure profiles will be recorded using a Tekscan Pressure Mat and plantar weight-bearing foot images will be recorded. Additionally, patient charts will be monitored over the course of the study to identify rate of infection, surgical intervention, and amputation and for one year following completion of the study to assess ulcer recurrence rates.

**Specific Aim 2:** To assess compliance and patient satisfaction with an oral immunonutrition supplementation regimen in diabetic patients with chronic, non-healing, lower-extremity wounds.

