#### **h. Statistical Analysis**

Summary statistics will be used to summarize measurements and assessed for unadjusted differences across treatment condition. Student's t-tests will be used for continuous measures, exact binomial tests for dichotomous measures, and chi-square tests for categorical measures.

The main outcome of interest is the proportion of wound closed at the end of 6 weeks which we will model in a generalized linear models framework

$$E[g(y_i)] = \beta_0 + Trt_i\beta_1 + Z_i\gamma$$

where  $y_i$  is the outcome measure of interest of the  $i$ th participant,  $Trt_i$  is an indicator variable of whether the participant was assigned to the treatment condition,  $Z_i$  is a vector of covariates for which we will adjust the model (i.e., initial wound size, diabetes etiology, sex, race, and age), and  $\gamma$  is a vector of regression parameters. We have written the outcome in terms of a link function ( $y_i$ ) to emphasize that we will estimate a linear regression model (identity function) as well as a zero-one augmented beta regression model for which we will choose from among several link functions (logit, log, log-log, and complementary log-log). Anticipating that we will have outcomes of exactly 0% or 100% reduction of the wound size, we will model the transformed outcome

$$y_i^* = \frac{99y + 0.5}{100}$$

Our focus is on the null hypothesis  $H_0: \beta_1 = 0$ . We will evaluate this null hypothesis using a Wald test of the parameter based on an appropriate variance estimate – chosen from model-based, sandwich, or sandwich based on an evaluation of the implied dispersion properties of the model-based variance estimator.

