Other secondary outcome variables to be modeled include the time to complete healing (Cox proportional hazards regression), rate of closure (Cox proportional hazards regression), presence of infection (binary regression), and need for surgery (binary regression). Cox proportional hazards models will be used to interpret the relative hazards between treatment conditions. The proportional hazards assumption will be checked using Schoenfeld residuals and accelerated failure time (parametric) regression models will also be evaluated. Binary outcomes will be modeled using various link functions (logit and log). Exponentiated coefficients for logit-link models will be interpreted as odds ratios, and exponentiated coefficients from log-link models will be interpreted as risk ratios. Binary outcomes may be relatively rare, and so we will also

estimated binary models using exact statistics. In addition, we will investigate bias through estimation of bias-corrected models.

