**Plan for management of unplanned and/or emergent surgery:**

If a wound of a patient enrolled in the treatment arm is progressing more rapidly than expected, as determined by the wound care provider, the provider will withdraw the patient and instruct them to discontinue supplementation immediately in preparation for surgery. Additionally, all patients will be flagged as participating in this research study in EPIC with details on the supplements involved. There will be an explicit note that the PI of the study should be contacted prior to any surgical procedure to discuss the timing of the surgery and discontinuation of the supplements. If it is not possible for the patient to discontinue the supplementation 2 weeks prior to surgery, all relevant parties (PI, surgeon, anesthesia) will be notified of the patient's involvement in the study and discuss additional potential risks of surgery and a patient-specific strategy for management of these risks. The study coordinator will review the charts of patients included in the supplement arm daily and will facilitate this communication between parties, if necessary.

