#### Directions:

Observe and measure the pressure ulcer. Categorize the ulcer with respect to surface area, exudate, and type of wound tissue. Record a sub-score for each of these ulcer characteristics. Add the sub-scores to obtain the total score. A comparison of total scores measured over time provides an indication of the improvement or deterioration in pressure ulcer healing.

LENGTH X WIDTH (in cm  )	0	1	2	3	4	5	Sub-score
	0	< 0.3	0.3 – 0.6	0.7 – 1.0	1.1 – 2.0	2.1 – 3.0	
EXUDATE AMOUNT	0	1	2	3	4	5	Sub-score
TISSUE TYPE	0	1	2	3	4	5	Sub-score
							TOTAL SCORE

**Length x Width:** Measure the greatest length (head to toe) and the greatest width (side to side) using a centimeter ruler. Multiply these two measurements (length x width) to obtain an estimate of surface area in square centimeters (cm^2). Caveat: Do not guess! Always use a centimeter ruler and always use the same method each time the ulcer is measured.

**Exudate Amount:** Estimate the amount of exudate (drainage) present after removal of the dressing and before applying any topical agent to the ulcer. Estimate the exudate (drainage) as none, light, moderate, or heavy.

**Tissue Type:** This refers to the types of tissue that are present in the wound (ulcer) bed. Score as a "4" if there is any necrotic tissue present. Score as a "3" if there is any amount of slough present and necrotic tissue is absent. Score as a "2" if the wound is clean and contains granulation tissue. A superficial wound that is reepithelializing is scored as a "1". When the wound is closed, score as a "0".

- 4 – Necrotic Tissue (Eschar):** black, brown, or tan tissue that adheres firmly to the wound bed or ulcer edges and may be either firmer or softer than surrounding skin.
- 3 – Slough:** yellow or white tissue that adheres to the ulcer bed in strings or thick clumps, or is mucinous.
- 2 – Granulation Tissue:** pink or beefy red tissue with a shiny, moist, granular appearance.
- 1 – Epithelial Tissue:** for superficial ulcers, new pink or shiny tissue (skin) that grows in from the edges or as islands on the ulcer surface.
- 0 – Closed/Resurfaced:** the wound is completely covered with epithelium (new skin).

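### The closure outcomes ignore how the ulcer closed, so early surgical closure can count as healing and an amputated ulcer could be entered as 100% closed

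*Combined protocol and SAP*

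**What the plan says.** **Closure outcomes.** Section 6e (Study Endpoints) gives the primary definition: "Complete wound closure will be defined as skin reepithelialization without drainage or dressing requirements confirmed at two consecutive study visits 2 weeks apart". Section 6h (Statistical Analysis) names as its target "The main outcome of interest is the proportion of wound closed at the end of 6 weeks", measured once, with no confirming visit. It expects complete closures among the data: "Anticipating that we will have outcomes of exactly 0% or 100% reduction of the wound size, we will model the transformed outcome". Among the other models it lists "time to complete healing (Cox proportional hazards regression", with no censoring or competing-event rule. Appendix 2 (PUSH Tool 3.0) says of the tissue sub-score "When the wound is closed, score as a" zero, and its chart labels a total of 0 as healed. None of these places mentions a procedure on the ulcer.

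**Surgery and amputation.** Specific Aim 1b in Section 2 has charts reviewed during the study to "identify rate of infection, surgical intervention, and amputation". Section 6i lists both rates as key data, and 6h models need for surgery as a separate binary outcome. Neither is linked to closure.

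**Withdrawal.** Section 6k lets the provider remove a patient in either arm whose wound is progressing fast and is expected to need surgery within the 6 weeks. This is at the provider's discretion, from a list stated to be non-exhaustive. Data up to that point may be used; no failure rule is given. The surgery plan in Section 9 is firmer but one-sided. It begins "If a wound of a patient enrolled in the treatment arm is progressing more rapidly than expected" and then directs withdrawal. It also foresees operations for which the supplements could not be stopped 2 weeks beforehand.

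**The concern.** The healing comparison is meant to show whether the supplement helps ulcers heal. The plan treats surgery and amputation as adverse outcomes, and Section 2 names limb salvage among the hoped-for benefits. Yet a patient whose ulcer was operated on could be a bad result for need for surgery and a good one for healing, and nothing in the plan resolves the conflict.

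The withdrawal provisions add a second difficulty. Treated patients heading for surgery are to be withdrawn, while for controls this is optional. The same clinical course may give missing data in one arm and a scored wound in the other. With no rule set in advance, someone must decide how to score each case after seeing it, in a trial of 30 patients where one patient is a visible share of an arm.

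**Working it through.** **Inputs.** 15 patients per arm (6c); wound checks at weeks 2, 4 and 6 (6f); the closure definition (6e); proportion closed and its transform y* = (99y + 0.5)/100 (6h); PUSH scoring (Appendix 2). The plan gives no closure rate, surgery rate, significance level or power, so it has no figure to reproduce. All counts and rates in steps 4 to 6 are assumed.

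**Step 1: timing.** Closure can be confirmed only at weeks 2 and 4 or at weeks 4 and 6. A surgical site must therefore be epithelialized, dry and undressed by week 4 at the latest, and at the paired visit as well. Only early procedures can meet the primary definition.

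**Step 2: three hypothetical records under the written rules.**

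| Record | Primary endpoint | Proportion closed y | y* |
|---|---|---|---|
| Ulcer excised and sutured in week 1; site epithelialized, dry and undressed at weeks 4 and 6 | Closed | 1.0 | 0.995 |
| Toe bearing the ulcer amputated in week 3 | Very unlikely: the site would have to qualify one week later and again at week 6, and the ulcer itself has arguably not reepithelialized | 1.0 if the absent ulcer is entered as zero area; the plan does not say | 0.995 if so |
| Ulcer 80% closed on standard care | Not closed | 0.8 | (79.2 + 0.5)/100 = 0.797 |

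The first record is a success under the rule as written. The second depends on how silence is read. Either could outrank the third on proportion closed. For PUSH, an absent ulcer gives a size sub-score of 0; a total of 0 also needs exudate and tissue sub-scores of 0.

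**Step 3: size per patient.** On the closure rate, 1/15 = 6.7 points. On y*, scoring a patient 100% instead of 0% moves the arm mean by (0.995 - 0.005)/15 = 0.066, and by less if the alternative is partial closure.

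**Step 4: illustration.** Assume 9/15 treated and 3/15 control patients close without surgery, and k of the other controls have an operation. Treated minus control difference in points, with two-sided Fisher p:

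| k | Scored not closed | Scored closed | Excluded |
|---|---|---|---|
| 1 | 40.0 (0.060) | 33.3 (0.139) | 38.6 (0.060) |
| 2 | 40.0 (0.060) | 26.7 (0.272) | 36.9 (0.067) |
| 3 | 40.0 (0.060) | 20.0 (0.466) | 35.0 (0.121) |

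From an assumed 7/15 v 1/15 (p = 0.035), one control scored closed gives 7/15 v 2/15 (p = 0.109). Whether one patient crosses 0.05 depends on the starting counts.

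**Step 5: direction.** Start again from 9/15 v 3/15, a difference of 40.0 points.
- One operated control scored closed: 60.0 - 26.7 = 33.3.
- One treated non-closure withdrawn and dropped: 9/14 - 3/15 = 64.3 - 20.0 = 44.3.
- Both together: 64.3 - 26.7 = 37.6.
- One operated treated patient kept and scored closed: 10/15 - 3/15 = 66.7 - 20.0 = 46.7.

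The difference can move either way.

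**Step 6: frequency.** The chance of at least one operated patient among n is 1 - (1 - p)^n. For assumed p = 1%, 3%, 5% and 10%, n = 30 gives 26%, 60%, 79% and 96%; n = 15 (one arm) gives 14%, 37%, 54% and 79%. These are upper bounds for misclassification. The operation must also close or remove the study ulcer, the patient must stay in follow-up, and the result must be recorded as closed.

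**The case against.** The plan is silent on these cases; it does not say that they count as healed. The primary definition asks for much more than the absence of an open wound, and it excludes nearly all amputations and late operations. Section 6k covers both arms and its grounds are open-ended, so many patients heading for surgery could leave before any post-operative score exists. Their outcomes would be missing, not healed. Study care is debridement, dressing and offloading, so elective excision and suture lies outside it. The Section 9 plan exists to stop supplements before surgery, and controls have none to stop. The number of cases in a 30-patient pilot is likely to be small.

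Most of this stands, and it limits the point. It does not remove it. An early surgical closure still meets the definition as written. The proportion-closed analysis has no confirming visit to protect it. Discretionary withdrawal cannot guarantee that operated patients leave, and Section 9 itself foresees surgery at short notice. Where patients do leave, the plan gives no rule for their outcome.

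A fair further objection is that a score of 0, the last pre-operative value and competing-event handling are all defensible. That is a reason to choose one beforehand and report another as a sensitivity analysis.

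**Conclusion.** The point holds as a gap in the endpoint definition that should be closed before the data are seen. An ulcer closed surgically early enough satisfies the primary rule. An ulcer removed by amputation or surgery could be entered as 100% closed in the week-6 analysis. Each such patient moves an arm's closure rate by up to 6.7 points. The frequency is not given and is probably low; the closure counts and surgery rates used above are assumptions.

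Three stronger readings are not supported.
- A reader might infer that an amputated ulcer will be counted as healed. On the primary endpoint this is close to excluded; on proportion closed and PUSH it is one interpretation of silence.
- A reader might infer from Section 9 that false successes fall mainly among controls and so dilute or reverse the contrast. The documents do not say in which arm operations will occur or how they will be recorded, and step 5 shows shifts both ways.
- A reader might take 26% to 96% as the chance of a misclassified result. Those figures are for any operation, at assumed rates.

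**What to change.** Add to 6e and 6h, for both arms:

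- Closure counts only if reached without amputation of the part bearing the study ulcer and without surgical closure, excision or grafting of it. Routine sharp debridement is excepted. The same condition applies before a PUSH total of 0 is read as healed.
- A patient who has such a procedure before confirmed closure, or who is withdrawn because such surgery is expected, is analysed as not closed on the primary endpoint. In the time-to-healing model this is a competing event: no healing event is counted, and the patient stays in the risk set to week 6.
- For proportion closed, score these patients 0, with a sensitivity analysis using the last pre-operative measurement.
- From the chart review already planned, record procedure type, date and whether the study ulcer was involved. Report the counts by arm.

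Including patients withdrawn for expected surgery matters. Without them, an operated control would score as a failure while a treated patient withdrawn beforehand could stay missing.

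This concerns scoring only and changes nothing about who is operated on or withdrawn. It costs a definition sentence, a few lines of analysis code and a little more abstraction, since 6i now lists only rates of surgery and amputation. The observed closure rate may be slightly lower.

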**f. Procedures Involved**

1. A research coordinator within the Prisma Health Orthopedics department will review weekly clinic schedules of participating providers at the Wound Healing Center to flag patients who may qualify for the study and are scheduled for an upcoming office visit. The provider scheduled to see the patient will be informed of potential subjects for inclusion.
2. At the office visit, the provider seeing the patient will inform the patient of the research study, screen to ensure eligibility criteria are met, and, if appropriate, consent the patient to participate in the study. The study will be thoroughly explained to the subject and all questions/concerns will be addressed. Research team members will be available to assist if the patient agrees to participate with the provider.

- a. Note: If the patient has not had an ECG (within 3 months of study enrollment), a lipid panel (within 3 months of study enrollment), a CMP (within 3 months of study enrollment, an INR/PT (within 3 months of study enrollment), and/or an A1c lab (within 6 months of study enrollment) these will be performed to confirm normal parameters prior to continuation of study activities. If any labs or ECG are required, results will be reviewed by the provider and the patient will resume study activities at their next scheduled visit.
3. The provider will document wound characteristics via the PUSH Tool 3.0 (Appendix 2). Plantar pressure profile readings will be obtained using a Tekscan Pressure Mat and clinical plantar weight-bearing images will be captured. The provider will verify and document concomitant medications in the patient's chart. The provider will visualize and evaluate any additional wounds that are present and record characteristics in the patient's chart.
4. The patient will be randomized to the control group or treatment group via a pre-defined randomization table in which subject IDs are already assigned as belonging to either group.
  - a. If randomized to the control group (SOC only), patients will receive standard of care defined as sharps debridement, appropriate dressing, and offloading. If randomized to the treatment group (SOC + Immunonutrition), subjects will receive standard of care defined as sharps debridement, appropriate dressing, and offloading in addition to a 6-week supply of Omega-3 fatty acids (soft gel form, 2 pills per day, total of 1.68 grams) and L-Arginine/Vitamin C (powder form, to be mixed with 8 oz liquid, 1 scoop once daily, total of 4.5 grams L-arginine and 500 mg vitamin C). Subjects will also be provided a compliance log with detailed instructions for taking and tracking supplements.
5. Patients will be scheduled for biweekly wound checks with their provider (weeks 2, 4, 6). Wound characteristics will be documented at each follow up visit using the PUSH Tool 3.0, images of the wound will be obtained, and an interval history and physical exam will be documented. The provider will verify and document concomitant medications in the patient's chart. The provider will visualize and evaluate any additional wounds that are present (new or present at time of enrollment) and record characteristics in the patient's chart. Patients will complete a questionnaire detailing their pain level (VAS), symptoms experienced during the treatment phase, and any unscheduled visits to emergency departments/urgent care centers. This will be completed via a paper survey in clinic during their office visit (Appendix 4). On weeks where an office visit is not scheduled (weeks 1, 3, 5), a research coordinator will call the patient and collect survey responses (Appendix 3).
6. At the final office visit (week 6), plantar pressure profiles will be recorded via the Tekscan Pressure Mat, and clinical plantar weight-bearing images will be captured. Patients randomized to receive the oral immunonutrition supplementation will complete an additional survey detailing their satisfaction with the treatment plan and any additional thoughts they would like to share (Appendix 5) and return the completed compliance log

(Appendix 6). Patients in the treatment arm will have CMP and lipid panel labs drawn at this timepoint or within 3 months of study completion.

7. A follow-up safety visit will be conducted by the provider for patients randomized to the treatment group 6-8 weeks after the week 6 office visit. This visit is more than 5 half-lives after supplementation discontinuation and will allow for capture of adverse events that may occur after completion of dosing. The wound will be visualized during this visit. Adverse events and wound details will be documented in the patient's chart. This visit will be conducted in-office if the patient is already scheduled to see their provider within the visit window. If the patient is not scheduled to see their provider, this visit may be conducted virtually through EPIC.
8. Patient charts will be monitored throughout the patient's participation in the study for any signs of infection, unscheduled visits, calls to the provider, and/or onset of severe adverse events. Patient charts will continue to be monitored for one year following the completion of the study to assess ulcer recurrence rates.

The schedule of events is outlined below and is pictured in Appendix 1:

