**Visit 3: 6 Week Follow-up/Completion Visit (Third visit after completing 42 days of oral immunonutrition):**

- Provider documents characteristics of wound via PUSH Tool 3.0, obtains plantar pressure profile reading, captures clinical photos, obtains interval history, performs interval physical exam, and verifies and documents concomitant medications.
- Provider visualizes and evaluates any additional wounds that are present and records characteristics in the patient's chart.
- Patient completes questionnaire in clinic (VAS, experienced symptoms since enrollment, review of supplement compliance).
- Patient completes satisfaction survey detailing their experience with supplementation (if applicable).
- Patient returns compliance log (if applicable).
- Provider orders CMP and lipid panel labs to be drawn at this timepoint or within 3 months of study completion.

**Phone Call 4: (Final Safety Follow-up, 6-8 weeks after completing oral immunonutrition, if randomized to treatment group):**

- Provider reviews and records adverse events experienced after supplement discontinuation and visualizes wound.

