### **9) Safety Monitoring Plan**

#### Laboratory Monitoring:

Periodic laboratory and ECG monitoring will be performed to assess safety of the oral supplement as detailed below:

**Lipid panel monitoring:** patients are eligible for study participation if they have had a lipid panel performed within 3 months of study enrollment. An additional lipid panel will be performed at study conclusion (6-week timepoint or within 3 months of study completion) for patients enrolled in the treatment arm.

**Blood glucose monitoring:** blood glucose is routinely monitored in diabetic patients at our institution. This data will be reviewed in the patients' charts as they become available, and the investigators will be alerted to any abnormalities.

**Serum chemistry parameters and hepatic enzymes:** patients are eligible for study participation if they have had a CMP performed within 3 months of study enrollment. An additional CMP will be performed at study conclusion (6-week timepoint or within 3 months of study completion) for patients enrolled in the treatment arm. Patients will have an INR/PT

performed at the time of study enrolled (if not within the past 3 months) to confirm no hepatic impairment.

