#### **Office Visit 3**

Week 6/Completion visit

After 42 days of oral immunonutrition  
\*Patients in treatment arm return compliance log, complete satisfaction survey, and have lipid panel and CMP labs drawn (or within 3 months of study completion) \*

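### The only scheduled follow-up CMP and lipid panel may be drawn up to about 13 weeks after a completer's last dose, too late to show reversible on-treatment changes

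*Combined protocol and SAP*

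**What the plan says.** Section 6.f, step 6 sets the timing for the treatment arm: "Patients in the treatment arm will have CMP and lipid panel labs drawn at this timepoint or within 3 months of study completion". The Visit 3 entry in the same section repeats the window: "Provider orders CMP and lipid panel labs to be drawn at this timepoint or within 3 months of study completion". Appendix 1, Office Visit 3 says treated patients "have lipid panel and CMP labs drawn (or within 3 months of study completion"). Section 9 (Laboratory Monitoring) and section 12 give the same choice of times. No other CMP or lipid panel is scheduled after baseline, and nowhere is the time since the last dose capped.

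Week 6 is treated as completion. The Visit 3 heading reads "6 Week Follow-up/Completion Visit (Third visit after completing 42 days of oral immunonutrition"), Appendix 1 calls it "Week 6/Completion visit", and Specific Aim 1 gives participation as 6 weeks.

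Section 9 states the purpose of these tests: "Periodic laboratory and ECG monitoring will be performed to assess safety of the oral supplement as detailed below". Section 7 lists increased ALT and AST among the possible effects of the omega-3 product, and says that the risks of this combination are unknown.

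Section 6.f, step 7 adds a safety follow-up for treated patients 6 to 8 weeks after week 6. Of its timing it says: "This visit is more than 5 half-lives after supplementation discontinuation". If no office visit is already booked, "this visit may be conducted virtually through EPIC". No laboratory test is attached to it.

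**The concern.** The tests exist to show whether the supplements disturb liver enzymes, chemistry or lipids. For that purpose the informative time is during dosing or at its end. The protocol lets the single draw be taken long after exposure has stopped, so a transient change could have resolved before anyone looked.

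Other safety procedures do not fill the gap. Weekly surveys, adverse event calls and chart review pick up symptoms and whatever laboratory tests clinicians happen to order. The routine monitoring described in section 9 is of blood glucose. None of these is a scheduled test of liver enzymes or lipids, so a symptomless change in them is reliably seen only on this one draw.

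What is at stake is the descriptive safety record of a combination not previously studied together in humans. A table of normal values drawn at mixed and unrecorded times off treatment could be read as evidence of on-treatment safety, which it would not be.

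**Working it through.** **Inputs**
- Dosing: 42 days, ending at about the week 6 visit (section 6.f, Visit 3; Appendix 6).
- Completion: the week 6 visit (section 6.f, Visit 3; Appendix 1; Specific Aim 1).
- Latest draw: 3 months after completion (section 6.f, step 6; sections 9 and 12; Appendix 1).
- Safety follow-up: 6 to 8 weeks after week 6, stated to be more than 5 half-lives after discontinuation (section 6.f, step 7).

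**Step 1: the permitted window.** Three months is 3 × 365.25/12 = 91.3 days, or 91.3/7 = 13.0 weeks. Depending on the calendar months it is 89 to 92 days, or 12.7 to 13.1 weeks. With completion at the end of dosing, the lag from last dose to draw is about 0 to 13 weeks.

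**Step 2: the late end against the safety follow-up.** 13 − 8 = 5 weeks and 13 − 6 = 7 weeks. The laboratory draw may come 5 to 7 weeks after the visit meant to catch events following the end of dosing.

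**Step 3: what that means for exposure.** Take the protocol's half-life statement at its word and use the cautious end, 8 weeks (56 days).
- Implied half-life: below 56/5 = 11.2 days.
- Half-lives elapsed at 91 days: more than 91/11.2 = 8.1.
- Fraction remaining at 91 days: below 0.5^8.1 = 0.4%, against 0.5^5 = 3.1% at the follow-up.

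This assumes first-order elimination and one bound for all components. It describes exposure only. The documents give no rate or time course for enzyme or lipid changes.

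**Step 4: sensitivity to the meaning of completion.** If study completion meant the safety follow-up instead, the latest draw would be 6 + 13 = 19 to 8 + 13 = 21 weeks after the last dose. A patient who stopped supplements early but was still timed from week 6 could also exceed 13 weeks. Thirteen weeks is the conservative figure.

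**Step 5: effect on safety reviews.** Section 9 has the Data Safety Committee meet after every 5 enrolments, and section 6.d plans 30 patients in 6 to 9 months. If enrolment is even, 5 patients take 6/6 = 1 to 9/6 = 1.5 months. A 3-month delay then spans 3/1.5 = 2 to 3/1 = 3 review cycles, or 10 to 15 further enrolments before that patient's result is available.

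**The case against.** The strongest reply is that the late draw is an allowance and not the default. Every statement of the window names week 6 first, the provider orders the tests at that visit, and the patient is already in clinic. Most draws may well be timely, and the allowance guards against losing a value altogether. This stands as far as frequency goes: nothing in the documents says how many draws would be late. But nothing limits or records the lag either, and a make-up rule can protect against missing values without treating a 13-week value as equivalent to a week 6 value.

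A second reply is that the stakes are small. Controls have no scheduled follow-up laboratory tests, no formal laboratory analysis is planned, the baseline value may itself be up to 3 months old, the doses are described as below the cited limits, and hepatic impairment is excluded at entry. All of this is true, and it keeps the use of the data descriptive. The dose limits concern the components singly, however, and the old baseline makes a well-timed second value more important: a patient could have one value 3 months before enrolment, one 3 months after dosing, and none near exposure.

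A third reply is that the half-life calculation does not show when an enzyme rise would resolve. That is correct. The calendar window carries the point, and the exposure figure only shows how far past washout the late end lies.

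Finally, a week 6 draw comes too late to trigger the section 9 rule for stopping supplements in that patient. That also stands. The gain is in describing the treatment period and in informing committee reviews while enrolment continues.

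**Conclusion.** The concern holds. The treatment arm's only scheduled post-baseline CMP and lipid panel can be drawn 0 to about 13 weeks after a completer's last dose. At the late end the result can miss a symptomless, reversible change in ALT, AST or lipids, although it can still detect persistent or delayed injury.

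The 13-week figure rests on reading study completion as the week 6 visit, which the visit labels support; other readings lengthen it. The number of the 15 treated patients affected, and the speed at which any laboratory change would reverse, cannot be determined from the documents. The primary, secondary and tertiary outcomes are untouched. This should be changed because it weakens the stated purpose of the laboratory monitoring and is nearly free to correct.

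**What to change.** In section 6.f (step 6 and Visit 3), section 9, section 12 and Appendix 1 (Office Visit 3):
- Require the CMP and lipid panel at the week 6 visit, with a short allowance such as 7 days from the last dose. That is 7/91 = 8% of the window now permitted.
- Keep any later draw as a make-up or follow-up value, so that a missed draw is not lost.
- Record days from last dose to draw. List late draws separately from end-of-treatment results, with the count of each out of 15.
- For patients who stop early, draw the tests at the discontinuation visit or next scheduled visit where feasible, without requiring an extra visit. Word section 12 so that study funds cover that draw.

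The cost is protocol wording and one recorded variable. Completers are already in clinic at week 6 and the tests are already funded, so no test or visit is added for them. The price is slightly less scheduling flexibility, and some early stoppers may still have only a later value or none.
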